# 9.3 Populations for Analyses

The primary analysis will be intent-to-treat (ITT). Under this principle, the evaluable sample will include all participants who are randomized.

#### 9.4 Statistical Analyses

#### 9.4.1 General Approach

In general, descriptive statistics will be presented by treatment group. Dichotomous variables will be summarized as number (%). Percentages will be calculated based on the number of participants with available data for that variable. Continuous variables will be summarized by the mean and standard deviation (SD). Ordinal data will be presented as median (IQR).

#### 9.4.2 Analysis of the Primary Endpoint

The primary outcome is VPM, which is a continuous value greater than 0. It is collected at baseline, 1 week, 3, and 6 months post treatment period. The primary analysis will calculate the change from baseline. The statistical model will be a repeated measures model (SAS\* MIXED procedure with REPEATED subcommand). The model will include the following fixed effects: categorical visit (1 week, 3, and 6 months post treatment period) by treatment group (class variable) interaction, site, baseline aphasia severity score, baseline VPM and age. The estimated difference (95% confidence intervals) in change between each SET duration group and control

group will be reported as the primary analysis. The standardized mean difference for each SET duration versus control will also be reported and will be used to select the best dose of SET. Since this study is not powered for direct comparison with control, no p-values will be reported. Estimates of the change at 1-week and 6 months obtained from this model are exploratory analyses. Additionally, as an exploratory analysis, the combined SET duration versus control comparison will be tested at a two-sided alpha of 0.05.

#### 9.4.3 Missing Data

The primary analysis will be ITT. All participants randomized will be included in the primary analysis regardless of whether or not they dropped out or discontinued treatment. For the primary analysis, a repeated measures linear mixed model will be fit; this is considered an implicit imputation approach if at least 1 post-baseline assessment is available. However, if baseline is the only assessment available (or if baseline is missing but follow-up available), then a nearest neighbor approach will be used to impute the missing values.

#### 9.4.4 Pre-specified rule to select best SET duration

- 1- Highest standardized mean difference (effect size) in VPM from baseline to three months post treatment;
- 2- Adequate tolerability: group average participation in at least 80% of the treatment sessions; We will select the duration associated with the highest group average VPM at 3 months post treatment, but also had adequate tolerability.

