#### 9.0 Statistical Considerations

#### 9.1 Statistical Hypotheses

• Primary Endpoint:

VPM at 3 months post treatment

We hypothesize that, compared to participants who receive control, participants who receive SET for 3, 4.5, or 6 weeks for aphasia will have improved VPM at 3 months and that there is an optimal duration of SET therapy. However, this study was not designed to formally test

SET versus control. This study represents the first step in a series of studies which will ultimately test this hypothesis; however, for this study no formal hypothesis tests are planned. The primary analyses will be descriptive statistics of VPM at 3 months and will estimate the effect size of each SET duration and the pooled SET durations versus control adjusting for baseline.

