#### 9.2.2 Sample Size Considerations for Effect Size of SET versus Control group

For each treatment group versus control, we will estimate the standardized mean difference (effect size). The criterion needed to accept any duration is that the effect size is at least 0.36 (a "small" effect size). The rationale for this criterion is that if the pooled standard deviation estimate is large, because of the small sample size, then the effect size may be smaller than expected. We consider a 20% improvement from control to be the the minimum clinically important difference (MCID). This corresponds to an increase of 1 VPM based on our pilot data (20% of 5 VPM). Given the MCID and the common SD of change in the VPM estimate from pilot data (SD=2), the expected effect size is 0.5. However, with n=20 per group, the observed SD may be as large as 2.74 based on the one-sided upper 95% confidence interval for the common SD; thus, the observed effect size may be only 0.36.

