##### *Sample Size Considerations for Effect Size of SET versus Control group*

For each treatment group versus control we will estimate the standardized mean difference (effect size). The criteria needed to accept any duration is that the effect size is at least 0.36 (a “small” effect size). The rationale for this criteria is that if the pooled standard deviation estimate is large, because of the small sample size, then the effect size may be smaller than expected. We consider a 20% improvement from control to be the MCID. This corresponds to a 1 point improvement in VPM (5x20%=1). Given the MCID=1 and the common SD of change in VPM estimate from pilot data of 2, we expect the effect size to be  $\frac{1}{2}=0.5$ . However, with  $n=20$  per group, observed SD may be as large as 2.74 (i.e. a one-sided upper 95% confidence interval for  $SD=2$  is 2.74), thus the observed effect size may be only  $1/2.74=0.36$ .

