## 7. ANALYSIS OF THE PRIMARY ENDPOINT

The primary outcome is VPM which is a continuous value greater than 0. It is collected at baseline and after 3 months post treatment. The primary analysis will calculate the change in average VPM (from the Narrative Story Telling Task and Procedural Story Telling Task) from baseline. The statistical model will be a repeated measures model (SAS® MIXED procedure with REPEATED subcommand). The model will include the following fixed effects: categorical visit (1 week, 3, and 6 months post treatment period) by treatment group (class variable) interaction, site, baseline aphasia severity score (centrally scored), baseline VPM and age. The estimated difference (95% confidence intervals) in change between each SET duration group and control group will be reported. The standardized mean difference for each SET duration versus control will be used to select the best dose of SET. Since this study is not powered for direct comparison with control, no p-values will be reported.

Empirical robust sandwich estimators will be used to account for the randomization procedure in order to appropriately estimate the marginal treatment effect. The unstructured covariance matrix for repeated observations within subjects will be used. In case the model will not converge, the maximum-likelihood (ML) estimation method will be used instead of the default restricted ML (REML). If the model still does not converge, a simpler covariance structures with less parameters will be used, according to the following order: heterogeneous autoregressive(1) (ARH(1)), heterogeneous compound symmetry (CSH), autoregressive(1) (AR(1)), and compound symmetry (CS). The estimated means at the 3 month post visit of the change from baseline in VPM will be compared for the SET 3 week group versus control, SET 4.5 week versus control, SET 6 week versus control, and the combined SET durations versus control. The SAS code for this analysis is as follows:

```
PROC MIXED EMPIRICAL;
  CLASS SUBJID ARM VISIT CENTER;
  MODEL CHANGE=ARM|VISIT CENTER BASE_WABAQ BASE_VPM AGE;
  REPEATED VISITNUM / TYPE=UN SUBJECT=SUBJID R RCORR;
  LSMEANS ARM*VISIT/ cl;
RUN;
```

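### The dose-selection rule names two different quantities without saying which prevails, and leaves out the plan's own 0.36 acceptance criterion

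*Protocol*

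**What the plan says.** The selection rule has the same wording in Protocol 9.4.4 and SAP 9. It lists two criteria and then a sentence that makes the choice.

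- Criterion 1: "Highest standardized mean difference (effect size) in VPM from baseline to three months post treatment". Control is not mentioned.
- Criterion 2: group average participation of at least 80% of sessions.
- The choice: "We will select the duration associated with the highest group average VPM at 3 months post treatment, but also had adequate tolerability".

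Other sections also say how the dose is chosen or what a duration must achieve:

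- Protocol 9.4.2 says the standardized mean difference for each duration versus control "will also be reported and will be used to select the best dose of SET". SAP 7 agrees: "The standardized mean difference for each SET duration versus control will be used to select the best dose of SET".
- The model in SAP 7 has change from baseline as its outcome and adjusts for baseline VPM: "MODEL CHANGE=ARM|VISIT CENTER BASE_WABAQ BASE_VPM AGE".
- Protocol 9.1 opens its account of the primary analyses with "The primary analyses will be descriptive statistics of VPM at 3 months and will estimate the effect size of each SET duration", and goes on to a comparison with control adjusted for baseline.
- Protocol 9.2.2, on sample size, sets a floor: "The criterion needed to accept any duration is that the effect size is at least 0.36". SAP 4 says the same: "The criteria needed to accept any duration is that the effect size is at least 0.36". Neither 9.4.4 nor SAP 9 repeats it.

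The primary objective (Protocol 3.0, SAP 1) is to estimate the dose with the highest effect size on VPM.

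**The concern.** A group average of VPM at 3 months is a level. Read literally, it has no baseline adjustment, no control comparison and no SD. A standardized mean difference in change versus control has all three. Chance differences between arms in starting VPM pass straight into the first quantity and are largely removed from the second, so the two can rank the durations differently. Both will be available at the end of the trial, because Protocol 9.1 makes descriptive statistics of 3-month VPM a primary output alongside the effect sizes.

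The rule also omits the 0.36 floor and does not say what follows if no duration reaches it. Read alone, it names a winner from among the tolerable arms even when every effect size is below 0.36.

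No formal hypothesis test is planned for the primary comparisons, so this rule is the trial's main decision. Protocol 9.2.1 says a dedicated comparison study will follow once the best dose is defined. A choice between two readings made after the results are known would not be pre-specified.

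**Working it through.** **The plan's own figure.** The 0.36 comes from the one-sided upper 95% limit for an SD of 2 with 20 in a group: √(19 × 2² / χ²₀.₀₅,₁₉) = 2.741, and 1/2.741 = 0.365. The stated 2.74 and 0.36 reproduce. This uses 19 degrees of freedom, that is, one arm. Pooling two arms (38) would give 2.47 and 0.40, which is one reason to name the SD in the rule.

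**Inputs.** From the pilot (Protocol 4.3.1, 15 people): VPM SD 3.9 at baseline, 4.8 at 3 months, 1.98 for change. From Protocol 4.1: 20 per arm. From Protocol 9.2.2: MCID 1 VPM.

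**Implied correlation.** r = (3.9² + 4.8² − 1.98²) / (2 × 3.9 × 4.8) = 0.917. With n = 15 the Fisher 95% interval is about 0.76 to 0.97.

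**Noise in each quantity.** The standard error of an arm's mean is 4.8/√20 = 1.07 VPM for the 3-month level, which exceeds the MCID, and 1.98/√20 = 0.44 for change.

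**An example with assumed values.** One arm starts at 6.0 and gains 0.8; another starts at 4.5 and gains 1.2. Their 3-month means are 6.8 and 5.7. With no change in control and an SD of 2, their effect sizes are 0.40 and 0.60. The 3-month mean picks the first arm and the effect size picks the second.

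**Simulation.** There were 40,000 four-arm trials per scenario, with normal data and the pilot SDs. The literal rule takes the highest raw 3-month mean. The adjusted rule takes the highest difference versus control, adjusted for baseline VPM, divided by the pooled SD of change. The true gains over control are assumed. The randomization balances site, age group and aphasia severity, not VPM itself. To allow for indirect balancing, 0%, 50% or 75% of the variance of between-arm baseline differences was removed. These percentages are also assumed, because the documents give no figure. Each cell gives literal correct / adjusted correct / disagreement, in %.

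| True gains (three doses) | 0% removed | 50% removed | 75% removed |
|---|---|---|---|
| 0, 0, 1 | 61 / 91 / 37 | 70 / 91 / 29 | 78 / 91 / 20 |
| 0, 0, 2 | 84 / 100 / 16 | 93 / 100 / 8 | 97 / 100 / 3 |
| 0.5, 0.75, 1 | 43 / 58 / 49 | 47 / 58 / 42 | 50 / 58 / 36 |
| All equal (disagreement only) | 51 | 46 | 38 |

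**Sensitivity to r** (gains 0, 0, 1; no balancing). At r = 0.76: 62 / 75 / 31. At r = 0.97: 61 / 99 / 39.

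**Sensitivity to the form of the effect size.** With unadjusted change and pairwise SDs, no balancing, and several sets of assumed gains, the effect size and the raw mean disagree in 37-41% of trials.

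**If the sentence means the adjusted mean.** All durations share one control arm, so with one common SD the two rankings are identical (0% disagreement). With a separate SD for each pair, they disagree in about 0-10%.

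**The 0.36 floor** (adjusted rule, no balancing). No duration reaches an observed 0.36 in 74% of trials if no dose works, in 30% if only one dose gains 1 VPM, and in 11% if all three gain 1 VPM.

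**The case against.** The strongest reply is that the intended quantity can be inferred. The objective, criterion 1, Protocol 9.4.2 and SAP 7 all point to the effect size. Protocol 9.2.2 defines that term as a comparison with control, and Protocol 9.1 ends with adjustment for baseline. The last sentence of the rule could be a loose summary of the two criteria. Likewise, a criterion needed to accept any duration implies that none is accepted if none meets it.

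This is a fair account of the likely intent. But no text gives it precedence, and the sentence that actually makes the choice, in the section headed as the pre-specified rule in both documents, says something else. The floor is in the plan but not in the rule.

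The size is also open to challenge. Every large figure needs the raw-mean reading. Disagreement among equal doses costs nothing. Loss is smaller than disagreement: with gains of 0.5, 0.75 and 1.0, the selected dose's mean true gain is about 0.07 VPM lower under the literal rule. With gains 0, 0, 1 the loss is 0.91 − 0.61 = 0.30 VPM. Normal data with mean 5 and SD 3.9 put about 10% of baseline values below zero, which VPM cannot take. These points limit the size but do not remove the contradiction.

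Finally, adjusted differences with confidence intervals are reported for every dose, so readers can see them all. That is correct, and the concern does not extend to the estimates.

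**Conclusion.** The concern holds. Protocol 9.4.4 and SAP 9 conflict internally and with Protocol 9.4.2 and SAP 7, and they omit the acceptance criterion in Protocol 9.2.2 and SAP 4.

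Followed literally, the rule selects less well on the primary objective. Where one dose is 1 VPM better, it is right in 61% of trials against 91% for the adjusted effect size, or in 70-78% against 91% with the assumed balancing. Under the adjusted-mean reading with one common SD, nothing is lost. The figures rest on SDs from 15 pilot participants, normal data, full follow-up at 20 per arm and assumed true gains.

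The direction does not depend on those details: a raw 3-month mean carries baseline noise that the adjusted effect size does not. Estimates and confidence intervals are unaffected. What is undetermined is which dose is declared best, and whether any is when none reaches 0.36.

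**What to change.** In both Protocol 9.4.4 and SAP 9:

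1. Replace the last sentence with a single rule. Among durations with mean participation of at least 80% and an effect size of at least 0.36, select the one with the largest baseline-adjusted standardized mean difference versus control at 3 months from the primary mixed model.
2. State the SD in the denominator, for example one common SD of change across arms.
3. State that no duration is selected if none meets both conditions.
4. Add the comparison with control to criterion 1, so that it matches Protocol 9.4.2 and SAP 7.

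These changes use only conditions already in the plan. They cost one or two sentences per document and need no extra data or participants. They should be made before unblinding. Because SAP 12 has an unblinded statistician fit the primary model semi-annually, the wording should be settled by people who have not seen those results.

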#### 9.4.5 Analysis of the Secondary Endpoint(s)

- Secondary Endpoints:
  - Quality of life assessment SAQOL-39g
  - Individual components of the primary outcome:
    - VPM on Narrative Story Telling Task
    - VPM on Procedural Story Telling Task

The SAQOL-39g will be analyzed similarly to the primary endpoint. The same approach will be used to define the analysis sample and handling of missing data. The mean change from baseline of each SET group will be compared to control with 95% confidence intervals. Since this study is not powered for direct comparison with control, no p-values will be reported.

#### 9.4.6 Safety Analyses

Monitoring Plan for Worsening in the Primary Outcome: If SET leads to substantially worse outcome than the no SET arm, early stopping may be considered. The unblinded statistician will fit the primary analysis model semi-annually in order to compare VPM between the combined SET durations versus No SET (one-sided  $\alpha$ =0.025). As part of this analysis, outliers will be explored to ensure that the results are not driven by a specific individual. Should the null hypothesis be rejected, an investigation of dose response among the SET arms based on qualitative evaluation (i.e. not statistical) when ordered in terms of dose level will occur. Should a dose response relationship be detected, the unblinded statistician will bring this to the attention of the DSMB and investigators.

All AEs and SAEs are summarized by preferred term according to the Medical Dictionary for Regulatory Activities (MedDRA) adverse reaction dictionary in terms of frequency of the event, number of subjects having the event. For the Closed DSMB report, severity, and relatedness to the treatment will also be shown by treatment group.

At the end of the trial, the cumulative incidences of the specific SAEs related to treatment, as well as all SAEs, will be compared across groups.

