# 3.0 Objectives and Endpoints

Objectives	Endpoint	Justification			
Primary					
To estimate the dose of SET for individuals with non-fluent aphasia that has the highest effect size on VPM.	Verbs per minute (VPM) at 3 months post-treatment/control period.	*See justification below			
Secondary					
To estimate the dose of SET for individuals with non-fluent aphasia that has the highest effect size on SAQOL-39g.	SAQOL-39g at 3 months post- treatment/control period	To assess if improvements in fluency from SET are related to gains in quality of life.			
Safety and Tolerability	Safety and Tolerability				
To assess the tolerability and safety of SET	Number of treatment sessions completed	Adequate tolerability would be completion of at least 80% of the treatment sessions.			

Exploratory	Adverse Events possibly/probably/definitely related to study treatment and Serious Adverse Events	Although this study intervention is low-risk, there is the potential for risk in any clinical trial.
To estimate the dose of SET for individuals with non-fluent aphasia that has the highest effect size on the WAB-R, CETI, and ASRS 3.0.	Scores at 3 months post-treatment/control period.	To assess if improvements in fluency from SET are related to gains in other speech and/or quality of life measures.
To estimate the effect of SET on VPM, WAB-R, SAQOL-39g at early and late time points.	1-week post and 6 months post	The primary time point of interest is the 3 months post, but the 1 week and 6 month post assessments will be explored to assess whether benefits are sustained over time

\*The primary endpoint for this trial is VPM at three months post-conclusion of SET or control. VPM is a measurable representation of spontaneous speech production. This primary endpoint was chosen for the following reasons:

- 1) Spontaneous speech is an important "real-life" aspect of language. It has a direct effect on conversation and social aspects of language, and directly informs on practical and meaningful elements of communication.
- 2) The use of verbs during spontaneous speech provides a reliable measure of language abilities and effectiveness of communication.
- 3) It is not surprising that many individuals with aphasia can achieve improved fluency during the SET session. However, for SET to have a clinical impact, it should lead to sustained benefits that remain after the therapy. Benefits that can last at least 3 months after therapy are highly important.

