#### 9.4.9 Tabulation of Individual Participant Data

Individual participant data will not be listed by measure and time point in the final analysis; however, individual participant listings may be included in Data and Safety Monitoring Board (DSMB) reports for purposes of monitoring trial quality.

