#### 10.7 Safety Oversight

A DSMB will provide the safety oversight for this trial. The DSMB meets annually to review safety data and trial progress.

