## **12. SAFETY ANALYSES**

### **Monitoring Plan for Worsening in the Primary Outcome**

If SET leads to substantially worse outcome than the no SET arm, early stopping may be considered. The unblinded statistician will fit the primary analysis model semi-annually in order to compare VPM between the combined SET durations versus No SET to detect worsening only (one-sided  $\alpha=0.025$ ). As part of this analysis, outliers will be explored to ensure that the results are not driven by a specific

individual. Should the null hypothesis be rejected, an investigation of dose response among the SET arms based on qualitative evaluation (i.e. not statistical) when ordered in terms of dose level will occur. Should a dose response worsening be detected, the unblinded statistician will bring this to the attention of the DSMB and investigators.

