### **Safety Monitoring**

The unblinded statistician at the DCU will produce semi-annual DSMB reports and at the request of the DSMB. The Closed Session DSMB reports will show tables by partially blinded treatment group. All serious adverse events will be summarized by “preferred term” and associated system-organ class according to the MedDRA dictionary and by treatment group in terms of frequency of the event and number of subjects having the event. For the DSMB report, severity and relatedness to the study drug will also be shown by treatment group.

At the end of the trial, the cumulative incidences of the specific SAEs related to treatment, as well as all SAEs, will be compared across groups.

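### A pooled test that finds VPM worse on SET must be reported to the DSMB only if a dose response is also judged present, so similar harm at all durations has no reporting step

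*Protocol*

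**What the plan says.** The monitoring plan for worsening opens with a general concern that carries no dose-response condition: "If SET leads to substantially worse outcome than the no SET arm, early stopping may be considered". The unblinded statistician refits the primary model semi-annually, compares the pooled SET arms with no SET at one-sided 0.025, and checks that outliers do not drive the result. If the null is rejected, dose response across the SET arms is examined "based on qualitative evaluation (i.e. not statistical").

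The Protocol then ends: "Should a dose response relationship be detected, the unblinded statistician will bring this to the attention of the DSMB and investigators". The SAP changes one word and keeps the condition: "Should a dose response worsening be detected, the unblinded statistician will bring this to the attention of the DSMB and investigators". Neither document says what happens when the test rejects and no dose response is seen.

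The other DSMB provisions are general:

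- Protocol 10.7: "The DSMB meets annually to review safety data and trial progress".
- SAP section 12, Safety Monitoring: "The unblinded statistician at the DCU will produce semi-annual DSMB reports and at the request of the DSMB". The by-arm content named there is serious adverse events.
- Protocol 9.4.9: "individual participant listings may be included in Data and Safety Monitoring Board (DSMB) reports for purposes of monitoring trial quality".
- SAP section 13 excludes interim analyses for success or futility and adds nothing on harm.

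None of these names the VPM comparison.

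**The concern.** The reporting step is narrower than the concern it serves. The plan worries about SET being worse than no SET and tests that with a contrast averaging the three durations. It then asks a different question, whether harm rises with duration, before anyone is obliged to tell the DSMB. If SET lowered VPM by a similar amount at every duration, the test would be well aimed and the condition would not be.

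Absence of a dose pattern among three arms of at most 20 is not evidence against such harm. With no criterion for the pattern, one person decides whether the DSMB hears of a rejected test. A DSMB that has not been told has no particular reason to use its right to ask for a report.

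**Working it through.** **The plan's own figure.** The monitoring plan states no operating characteristics. The SD used below comes from Protocol 9.2.2 (SD 2, 20 per group). The upper limit given there reproduces: 2 × √(19/χ²(0.05; 19 df)) = 2 × √(19/10.117) = 2.74, and 1/2.74 = 0.36.

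**One look at full enrolment.** With 60 SET and 20 control participants, the standard error of the pooled contrast is 2 × √(1/60 + 1/20) = 0.516. The probability of rejection is Φ(δ/0.516 − 1.96):

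- harm of 1 VPM (the plan's MCID): Φ(−0.02) = 49%
- harm of 1.5 VPM: Φ(0.94) = 83%
- harm of 2 VPM: Φ(1.91) = 97%

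With equal true harm and equal arm sizes, the ordering of the three SET means is independent of their average. Given rejection, strict ordering by duration (worsening from 3 to 4.5 to 6 weeks) therefore occurs in 1/3! = 1/6 of cases. The looser pattern (6 weeks worse than 3 weeks) occurs in 1/2. A 400,000-replicate simulation gave 16.5% to 16.7% and 50%. The condition thus says nothing about whether uniform harm is real. Even under graded harm of 0.5/1/1.5 VPM, only 58% of rejections show the strict ordering.

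**Repeated looks.** Assumptions: looks at 20, 30, …, 80 evaluable (80 participants over 4 years is 20 per year, or 10 per half-year), one outcome time, 1:1:1:1 in blocks of 4, pooled-variance t test at one-sided 0.025 at each look, and 100,000 trials per scenario. The last two columns count trials in which the condition is met at a look that also rejects.

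| True change at 3/4.5/6 weeks | Looks | Any rejection | Strict met | Loose met |
|---|---|---|---|---|
| 0/0/0 | seven | 7.6% | 1.8% | 4.4% |
| −1/−1/−1 | seven | 59.3% | 17.3% | 37.7% |
| −1/−1/−1 | up to 60 evaluable | 47.7% | 12.5% | 29.1% |
| −1/−1/−1 | four (20, 40, 60, 80) | 56.3% | 14.4% | 34.2% |
| −1.5/−1.5/−1.5 | seven | 86.9% | 28.2% | 58.2% |
| −1.5/−1.5/−1.5 | up to 60 evaluable | 76.2% | 21.7% | 48.3% |
| −0.5/−1/−1.5 | seven | 59.0% | 40.5% | 56.4% |

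For uniform harm of 1 VPM over seven looks, the share of rejecting trials with no reporting step is 1 − 37.7/59.3 = 36% (loose) to 1 − 17.3/59.3 = 71% (strict).

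**Timing.** The control group's 3-month visit falls at day 137 after randomisation (Protocol Table 2). At 20 per year, 20 × 137/365 = 7.5 participants are randomised but not yet evaluable, so about 67 of 80 are already randomised at 60 evaluable.

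**Effect of the SAP's EMPIRICAL standard errors.** A single-visit covariance-analysis proxy (four arms, two site terms, three covariates, t with N − 9 df, 40,000 trials, seven looks) gave:

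| Standard errors | Scenario | Any rejection | Strict met | Loose met |
|---|---|---|---|---|
| Sandwich | no effect | 15.2% | 3.4% | 8.7% |
| Sandwich | uniform −1 | 66.5% | 20.6% | 43.6% |
| Model-based | no effect | 7.9% | 1.7% | 4.4% |
| Model-based | uniform −1 | 56.8% | 16.4% | 36.1% |

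The proxy is not the specified repeated-measures model. It serves only to show the range of alert rates.

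**The case against.** The strongest reply is that the plan is silent, not prohibitive. The same unblinded statistician runs the test and writes the DSMB reports, the plan sits under a safety heading, and the early-stopping sentence has no dose condition. The result would probably reach the DSMB anyway. That is fair, and it is why the point is limited to what the plan requires. A probable communication is still not a commitment.

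Second, the condition may be a deliberate filter. The test is repeated without correction, the study is not powered against control, and the Protocol says "Although this study intervention is low-risk". The documents give no such purpose, so this is an inference. The trade-off is real, though: reporting every rejection raises alerts under no effect. But the filter blocks a uniform harm signal as readily as a false one, and the outlier check already guards against a single influential participant.

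Third, the sizes rest on hypothetical harm, an assumed look schedule and two readings of an undefined term. The uncontrolled pilot moved the other way (+1.11 VPM at 3 months). Late looks also change little. By 40 evaluable, with about 47 randomised, uniform harm of 1 VPM is rejected in about 33% of trials, with 8% to 19% meeting the condition. An explicit report would then be added in roughly a seventh to a quarter of such trials while much enrolment remains. At 0.5 VPM, only 15% are rejected by that stage. All of this stands as a limit on the practical size. None of it supplies the missing step.

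**Conclusion.** The concern holds on the text of both documents. A statistician who follows the rule exactly can reject the null for worsening and have no written duty to tell the DSMB, and uniform harm is the case most exposed.

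The 36% to 71% figure is an illustration that depends on SD 2, the assumed looks and the reading of dose response. The gap itself depends on none of these. Nothing here biases the primary estimate, the confidence intervals or the choice of duration. It should be fixed because it concerns participant safety and costs little to close.

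**What to change.** In Protocol 9.4.6 and SAP section 12, with identical wording, insert before the last sentence of the monitoring plan:

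*If the null hypothesis is rejected, the unblinded statistician will report the result to the DSMB, with the outlier review and the mean VPM change by SET duration as descriptive context, whether or not a dose response is seen.*

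Keep the existing last sentence, which then adds only the notification of investigators. The test and its alpha do not change. Whether to alter that provision, and any decision on stopping, stays with the sponsor and the DSMB.

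The cost is one sentence in two places and more false alerts. Over seven looks with no SET effect, alerts rise to about 15% of trials with sandwich errors (proxy), from 3% to 9% under the present condition. With model-based errors they rise to about 8%, from 2% to 4%. An alert prompts DSMB review and is not a stopping decision.
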